## 4. Study Objectives

### 4.1. Primary Objective

The primary efficacy objective is to test the hypothesis that at least one dose of LY2951742 (120 or 240 mg/month) is superior to placebo in the prevention of migraine headache in patients with episodic migraine. Superiority is defined as greater improvement for LY2951742 compared with placebo as measured by the overall mean change from baseline in the number of monthly migraine headache days during the 6-month double-blind treatment phase.

A migraine headache day is defined as any calendar day with a headache lasting longer than 30 minutes that meets the criteria for migraine or probable migraine (see endpoint definition in [Table CGAN. 5.1](#)).

### 4.2. Secondary Objectives

#### 4.2.1. Key Secondary Objectives

Key secondary objectives listed in [Table CGAN. 4.1](#) reflect comparisons of each LY2951742 dose with placebo.

Table CGAN. 4.1 List of Key Secondary Objectives and Their Endpoints

Objectives	Endpoints
To compare LY2951742 with placebo with respect to 50% response rate	The proportion of patients with reduction from baseline $\geq 50\%$ in monthly migraine headache days during the 6-month double-blind treatment phase
To compare LY2951742 with placebo with respect to 75% response rate	The proportion of patients with reduction from baseline $\geq 75\%$ in monthly migraine headache days during the 6-month double-blind treatment phase
To compare LY2951742 with placebo with respect to 100% response rate	The proportion of patients with reduction from baseline =100% in monthly migraine headache days during the 6-month double-blind treatment phase
To compare LY2951742 with placebo with respect to change in functioning	Mean change from baseline in the Role Function-Restrictive domain score of the Migraine-Specific Quality of Life Questionnaire version 2.1 (MSQ v2.1) (average of Months 4, 5, and 6)
To compare LY2951742 with placebo with respect to change in use of acute (abortive) migraine treatment	The overall mean change from baseline in the number of monthly migraine headache days requiring medication for the acute treatment of migraine during the 6-month double-blind treatment phase
To compare LY2951742 with placebo with respect to change in global severity of the migraine condition	Mean change from baseline in the Patient Global Impression of Severity (PGI-S) score (average of Months 4, 5, and 6)

#### 4.2.2. Other Secondary Objectives

The secondary objectives listed below in [Table CGAN. 4.2](#) reflect the comparison of LY2951742 (120 or 240 mg/month) with placebo.

Table CGAN. 4.2 List of Other Secondary Objectives and Their Endpoints

Other Secondary Objectives	Endpoints
To compare LY2951742 with placebo with respect to change in headache days	The overall mean change from baseline in the number of monthly headache days during the 6-month double-blind treatment phase
To compare LY2951742 with placebo with respect to change in moderate to severe headache days	The overall mean change from baseline in the number of monthly moderate to severe headache days during the 6-month double-blind treatment phase
To compare LY2951742 with placebo with respect to 30% response rate	The proportion of patients with reduction from baseline $\geq 30\%$ in monthly migraine headache days during the 6-month double-blind treatment phase
To compare LY2951742 with placebo with respect to distribution of response rates	Cumulative distribution of monthly migraine headache day response rates (0%, 5%, 10%, ..., 95%, 100%) during the 6-month double-blind treatment phase
To compare LY2951742 with placebo with respect to time to first 50% response	Time to first occurrence (in months) of a $\geq 50\%$ reduction from baseline in the number of monthly migraine headache days (Kaplan-Meier analysis)
To compare LY2951742 with placebo with respect to onset of effect	The initial month at which statistical separation in mean change from baseline in the number of monthly migraine headache days is demonstrated and maintained at all subsequent months through Month 6
To compare LY2951742 with placebo with respect to onset of 50% sustained response	The initial month at which statistical separation in the proportion of patients meeting at least a 50% reduction in monthly migraine headache days that is sustained at all subsequent months through Month 6
To compare LY2951742 with placebo with respect to maintenance of 50% response	The proportion of patients who maintain 50% response criteria for at least 3 consecutive months to the patient's endpoint during double-blind treatment phase. The proportion of patients who maintain 50% response criteria for 6 consecutive months during double-blind treatment phase
To compare LY2951742 with placebo with respect to changes in other efficacy parameters, specifically: 
 
• International Classification of Headache Disorders (ICHD) migraine headache day
 
• migraine attacks
 
• migraine headache hours
 
• headache hours
 
• severity of remaining migraines
 
	Overall mean change from baseline (during the 6-month double-blind treatment phase) on the following monthly measures: 
 
• ICHD migraine headache days
 
• migraine attacks
 
• migraine headache hours
 
• headache hours
 
• severity of remaining migraines
 

Other Secondary Objectives (cont.)	Endpoints (cont.)
To compare LY2951742 with placebo with respect to global assessment of illness	Overall Patient Global Impression-Improvement (PGI-I) rating during the 6-month double-blind treatment phase
To compare LY2951742 with placebo with respect to changes in disability and quality of life	Mean change from baseline on the following measures: 
 
• the Migraine Disability Assessment test (MIDAS) total score and individual items at Months 6
 
• the Migraine-Specific Quality of Life Questionnaire, version 2.1 (MSQ v2.1) total score, and Role Function-Preventive and Emotional Function domain scores (average of Months 4, 5, and 6)
 
 Descriptive summary at each visit for the following measure: 
 
• the HealthCare Resource Utilization (HCRU) and employment status
 

To evaluate patient satisfaction with medication	Satisfaction with medication using the Patient Satisfaction with Medication Questionnaire-Modified (PSMQ-M)
To compare LY2951742 with placebo with respect to safety and tolerability	Analysis of: 
 
• treatment emergent adverse events (TEAEs)
 
• discontinuation rates
 
• vital signs and weight
 
• electrocardiograms (ECGs)
 
• laboratory measures
 
• Suicidality using the Columbia Suicide Severity Rating Scale (C-SSRS)
 
• Other safety parameters
 

To evaluate immunogenicity of LY2951742	Throughout the study: 
 
• Development and consequences of anti-drug antibodies and neutralizing anti-drug antibodies to LY2951742
 

To evaluate pharmacokinetics of LY2951742	Serum concentrations of LY2951742
To evaluate pharmacodynamics (target engagement) of LY2951742	Plasma concentrations of CGRP
To assess changes in efficacy outcomes during Study Period IV as collected by electronic patient-reported outcomes (ePRO) diary data	In Study Period IV: 
 
• Mean changes from baseline in migraine headache days (SP III and SP IV combined)
 
• Time to first loss of response (in SP IV) among patients who meet the 50% response rate criteria at the end of the double-blind treatment phase
 
• Time to initiation of treatment with a migraine prevention medication (in SP IV)
 

Abbreviations: CGRP = calcitonin gene-related peptide; MHD = migraine headache day.

### 4.3. Exploratory Objectives

Some of the exploratory objectives are listed here.

[figure not shown]
**Table CGAN. 4.3 List of Some Exploratory Objectives and Their Endpoints**

Objectives	Endpoints
To explore pharmacogenetics	Analysis of genetic variation on response, safety, and tolerability to LY2951742 treatment
CCI	
To compare LY2951742 with placebo with respect to categorical changes in quality of life	Percentages of patients with 
 
• <math>\geq 50\%</math> improvement in MIDAS total score at Month 6
 
• change from baseline in MSQ Role Function-Restrictive domain <math>\geq 25</math> (average of Months 4, 5, and 6)
 

To compare LY2951742 with placebo with respect to the proportion of migraine headache days requiring medication for the acute treatment of migraine headache	Change from baseline in the proportion of monthly migraine headache days requiring medication for the acute treatment of migraine headache
To compare LY2951742 with placebo with respect to changes in symptomatology associated with migraine or probable migraine	Change from baseline in the number of monthly migraine headache days with 
 
• nausea and/or vomiting
 
• photophobia and phonophobia
 
• aura
 
• prodromal symptoms other than aura
 

To explore safety results during Study Period IV	Analysis of the following during Study Period IV: 
 
• FEAEs
 
• discontinuation rates
 
• vital signs and weight
 
• ECGs
 
• laboratory measures
 
• other safety parameters, including suicidality using the C-SSRS.
 

Abbreviations: CGRP = calcitonin gene-related peptide; C-SSRS = Columbia–Suicide Severity Rating Scale; FEAE = follow-up-emergent adverse event; ECG(s) = electrocardiogram(s); MIDAS = Migraine Disability Assessment test; MSQ = Migraine-Specific Quality of Life Questionnaire version 2.1; PD = pharmacodynamic(s); PK = pharmacokinetic(s).

## 5. A Priori Statistical Methods

### 5.1. Study Design

\*Eligibility period determined between a minimum of 30 days and a maximum of 40 days. Investigators may have up to 5 additional days (beyond the 40 days) if needed to schedule patients' Visit 3 appointment.

aPatients randomized to the 120 mg dose will receive a loading dose of 240 mg at the first injection only (Visit 3).

Approximately 240 enrolled patients roll-over to I5Q-JE-CGAP study (Open Label Extension) at visit 12

Abbreviations: SP = study period.

**Figure CGAN.5.1. Study I5Q-JE-CGAN protocol design.**

### 5.2. Determination of Sample Size

The study will enroll approximately 451 patients. Eligible patients will be randomized in blinded fashion in a 2:1:1 ratio to placebo (target of 225 patients), galcanezumab 120 mg/month (target of 113 patients), or 240 mg/month (target of 113 patients). With the assumption of a 15% discontinuation rate and an effect size of 0.36, it is estimated that this sample size will provide approximately 88% power that at least 1 dose of galcanezumab will separate from placebo at a two-sided significance level of 0.05 based on simulations using the Dunnett's test (Dunnett 1955). Assumptions in the simulations were based on the assumptions for global Phase 3 studies, with adjustment to reflect less dropout and less variability in a more homogenous Japanese study.

Approximately 902 patients may be screened to ensure randomization of 451 patients, with an estimated 383 patients completing the study.

### 5.3. Randomization and Treatment Assignment

Patients will be randomized in a blinded fashion to LY2951742 120 mg, 240 mg, or placebo with a randomization ratio of 2:1:1 (about 225 on placebo, 113 on LY2951742 120 mg, and 113 on LY2951742 240 mg). To achieve between-group comparability, the randomization will be stratified by baseline migraine frequency (<8 migraine headache days versus  $\geq$ 8 migraine headache days). To ensure an appropriate balance of low- and high-frequency migraine headache-day patients, the sponsor will stop enrollment of low-frequency patients, if the number exceeds an estimated 315.

### 5.4. Endpoints

#### 5.4.1. *Efficacy Endpoints*

Migraine and headache endpoints are defined in [Table CGAN. 5.1](#). Each month is defined as a 30-day period with migraine or headache measures normalized from the visit intervals.

Table CGAN. 5.1 Migraine and Headache Endpoint Definitions

Diagnosis	Definition/Criteria
Migraine headache	A headache, with or without aura, of $\geq 30$ minutes duration with both of the following required features (A and B): A. At least 2 of the following headache characteristics: 
 
• Unilateral location
 
• Pulsatile quality
 
• Moderate or severe pain intensity
 
• Aggravation by or causing avoidance of routine physical activity
 
 AND B. During headache at least 1 of the following: 
 
• Nausea and/or vomiting
 
• Photophobia and phonophobia
 
 (Definition adapted from the IHS ICHD-3 beta)
Probable migraine headache	A headache missing 1 of the migraine features in the IHS ICHD-3 beta definition such that 1 feature in criteria A is missing or 1 feature in criteria B is missing; that is, meet at least 2 A criteria and none of the B criteria, or meet 1 of the A criteria and at least 1 of the B criteria.
Migraine headache day	A calendar day on which a migraine headache or probable migraine headache occurred.
Migraine headache attack	Beginning on any day a migraine headache and/or a probable migraine headache is recorded, and ends when a migraine-free day occurs.
Non-migraine headache	All headaches of at least 30 minutes duration not fulfilling the definition of migraine or probable migraine.
Non-migraine headache day	A calendar day on which a non-migraine headache occurred.
Headache day	A calendar day on which any type of headache occurs, (including migraine headache, probable migraine headache, and non-migraine headache).
Migraine headache days with abortive (acute) medication use	Calendar days on which migraine or probable migraine occurs, requiring abortive (acute) medication.
ICHD migraine headache day	A calendar day on which a migraine headache occurs.

Abbreviations: ICHD = International Classification of Headache Disorders; IHS = International Headache Society.

Headache information will be collected via an electronic patient reported outcome (ePRO) diary. Patients will need to enter diary data daily beginning from Visit 2, continuing until Visit 14.

Information recorded in the ePRO diary, the possible responses and the assignment to the type of headache is presented in [Table CGAN. 5.2](#).

**Table CGAN. 5.2 ePRO Diary Questions, Responses, and Assignment to Headache Type**

QUESTION	RESPONSES	HEADACHE ASSIGNMENT
Q1. Yesterday, did you have a headache that lasted for thirty minutes or more?	Yes	Migraine if at least two migraine Criteria A's and at least one migraine Criteria B.
	No a	
Q2. Enter the total number of hours you had a headache yesterday.	Range 1 to 24	If $\geq 1$ , the headache will be counted as a headache day.
Q3. Yesterday, what was the worst headache pain?	Mild	
	Moderate	Migraine Criteria A
	Severe	Migraine Criteria A
Q4. Yesterday, was the headache throbbing or pounding?	Yes	Migraine Criteria A
	No	
Q5. Yesterday, was the headache just on the right or left side of your head?	Yes	Migraine Criteria A
	No	
Q6. Yesterday, was the headache made worse by your usual daily activity?	Yes	Migraine Criteria A
	No	
Q7. Yesterday, did the headache come with sensitivity to light and sound?	Yes	Migraine Criteria B
	No	
Q8. Yesterday, did you feel sick to the stomach or throw-up with the headache?	Yes	Migraine Criteria B
	No	
Q9. Yesterday, did you have your menstrual period (if female)?	Yes	
	No	
Q10. Yesterday, did you take any medicine for your headache?	Yes	Medication will only count as headache medication on a day a headache occurred.
	No	
Q11. Yesterday, did you take any medication for pain other than headache?	Yes	
	No	
Q12. Yesterday, did you experience aura?	Yes	
	No	
Q13. Yesterday, did you experience any warning symptoms other than aura (prodrome symptoms) that a migraine was coming?	Yes	
	No	

a If "No" is answered for Q1, then the patients will skip Q2 - Q6, only answer questions Q7 - Q13.

**Primary Measure: the Number of Monthly Migraine Headache Days**

The primary measure is the number of monthly migraine headache days. A migraine headache day is defined as a calendar day on which a **migraine or probable migraine** occurs.

The primary measure of the number of monthly migraine headache days will be summarized from the daily ePRO data for each patient in that period (including 30 days of daily data from the baseline period prior to randomization, 6 months of daily data during the treatment phase, and 4 months of daily data during the post-treatment phase).

The daily data will be aggregated, and the number of migraine headache days will be provided for each of the 30-day periods. In calculating the number of migraine headache days for each period, if the period is not equal to 30 days, the number of migraine headache days will be normalized by multiplying the number of migraine headache days by  $(30/x)$  where 'x' is the total number of non-missing diary days in the period.

For the baseline period (Visit 2 to Visit 3), once a patient becomes eligible before Visit 3 judged from the daily ePRO data (this is called **eligible day**), then all ePRO data after the eligible day to Visit 3 will be ignored.

Example: A patient has Visit 2 = 2016/Jan/1. He records diary on Jan/2 for his headache information on Jan/1. He records diary everyday (no missing data.) He records diary on Jan/31 for his headache information on Jan/30 which ends up as 5th migraine headache day during the baseline period (starting from Jan/1.) He becomes eligible for CGAN study (assuming all other eligibility conditions are met.) He goes to a site on Feb/ 4 (Visit 3) and gets 1st injection on the day. In this case **eligible day** is 2016/Jan/30. All diary data of Jan/1, Jan/2,..., Jan/30 will be used as baseline period data. All diary data of Jan/31, Feb/1, Feb/2, Feb/3 will be ignored. Diary data on Feb/4 (Visit 3) is used for Month 1 period data.

For the double blind period (SP III), Month 1 period data is based on headache information from Visit 3 up to on Visit 5 – 1 day. Month 2 period data is based on headache information from Visit 5 up to Visit 6 – 1 day. Month 3, to Month 6 will be defined similarly.

For the 4 months of the post-treatment period, the monthly interval will be derived as below. Firstly, the 2-month visit interval will be split into two one-month periods for efficacy measures. If the number of days between two visits (visit x + 1 date - visit x date + 1) is even, the first half will be in the first one-month period and the second half will be in the second one-month period. If the number of days between two visits is odd, then the days will be split similarly, but the first one-month period will have one day more than the second one-month period. Secondly, after the two-month visit intervals are split into two one-month periods, the monthly data will be derived in the same way for each one-month period as for treatment phase. For patients who discontinued early during the post-treatment phase, if the date of discontinuation is within 30 days of previous visit date, all data between the previous visit date and the discontinuation date will go to one monthly period; if the date of discontinuation is more than 30 days of the previous

visit date, then the first 30 days will be the first monthly period, and the rest will be considered as part of the second monthly period.

This approach to missing ePRO diary data assumes that the rate of migraine headaches per day is the same for days with missing and non-missing ePRO diary days, and it is missing at random (MAR). The same approach will also be applied to secondary and exploratory efficacy measures that are derived from ePRO data.

Example 1: A patient has 64 days between Visit 13 and Visit 14. He completes the study on Visit 14. Then he has

- 1st half month = ePRO diary data from day 1 to day 32
- 2nd half month = ePRO diary data from day 33 to day 64.

Example 2: A patient has 64 days between Visit 13 and Visit 14. He discontinues the study on Visit 14 (i.e., disposition is not marked as completed). Then he has

- 1st half month = ePRO diary data from day 1 to day 30
- 2nd half month = ePRO diary data from day 31 to day 64.

Example 3: A patient has 70 days between Visit 13 and Visit 14 (outside of visit allowance). He completes the study on Visit 14. Then all data will be captured and he has

- 1st half month = ePRO diary data from day 1 to day 35
- 2nd half month = ePRO diary data from day 36 to day 70.

Example 4: A patient has 70 days between Visit 13 and Visit 14 (outside of visit allowance). He discontinues the study on Visit 14 (i.e., disposition is not marked as completed). Then all data will be captured and he has

- 1st half month = ePRO diary data from day 1 to day 30
- 2nd half month = ePRO diary data from day 31 to day 70.

Example 5: A patient has 35 days between Visit 13 and Visit 14. He discontinues the study on Visit 14 (i.e., disposition is not marked as completed). Then he has

- 1st half month = ePRO diary data from day 1 to day 30
- 2nd half month = ePRO diary data from day 31 to day 35.

Example 6: A patient has 14 days between Visit 13 and Visit 14. He discontinues the study on Visit 14 (i.e., disposition is not marked as completed). Then he has

- 1st half month = ePRO diary data from day 1 to day 14
- 2nd half month = No ePRO diary data

Example 7: A patient has 14 days between Visit 5 and Visit 6. He discontinues the study on Visit 6. Then he has

- Month 2= ePRO diary data from day 1 to day 14

Additionally, if the compliance rate for each monthly interval is  $\leq 50\%$ , then all endpoints to be derived from the ePRO diary data for that one-month period will be considered missing. For the post-treatment phase, the derived one-month periods (resulting from splitting two-month visit interval) will be treated similarly. For a patient who discontinued early in the double-blind treatment phase or post-treatment phase, the compliance rate for the last month of that study period will be calculated with the denominator of the maximum of 30 and the total number of calendar days in that month, i.e.,  $\max(30, \text{the total number of calendar days in that month})$ . For the rest of months and the period, the compliance rate will be calculated as described in Section 5.5.7.

In the Example 7 above, diary compliance rate for Month 2 is less than 50% even if he has no missing diary for 14 days between Visit 5 and Visit 6. Note that he discontinues and the denominator is  $\max(30, 14) = 30$ . Hence, diary compliance rate =  $14/30 * 100 < 50\%$ . Hence Month 2 diary data is considered as missing.

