6.1. Inclusion Criteria

Patients are eligible to be included in the study only if they meet all of the following criteria at screening:

Patient and Disease Characteristics

- [1] Patients are 18 to 65 years of age (inclusive) at the time of screening.
- [2] Have a diagnosis of migraine as defined by International Headache Society (IHS) International Classification of Headache Disorders- (ICHD-) 3 beta guidelines (1.1 or 1.2) (HCCIHS 2013), with a history of migraine headaches of at least 1 year prior to Visit 1, and migraine onset prior to age 50.
- [3] Prior to Visit 1, have a history of 4 to 14 migraine headache days, and at least 2 migraine attacks per month, on average, within the past 3 months.
- [4] From Visit 2 to Visit 3 (prospective baseline period), have a frequency of 4 to 14 migraine headache days, and at least 2 migraine attacks per month. **To avoid biased reporting, patients must not be told the number of migraine headache days on which study qualification is based.**
- [5] From Visit 2 to Visit 3 (prospective baseline period), must achieve sufficient compliance with ePRO daily headache entries, as demonstrated by completion of at least 80% of daily diary entries.

Informed Consent and Patient Agreements

- [6] Are able and willing to give signed informed consent, and in the case of patients under 20 years old, informed consent signed by a parent or guardian.
- [7] Are reliable and willing to follow study procedures, including all follow-up visits.

- [8] Women of childbearing potential must test negative for pregnancy at the time of enrollment, based on a serum pregnancy test. Women of non-childbearing potential are defined as follows:
- 1) Confirmed spontaneous amenorrhea with evidence of cessation of menses for at least 12 months and a follicle-stimulating hormone(FSH) level >40 mIU/mL at screening,
 - Or
 - 2) Confirmed from medical record to be infertile due to congenital or acquired condition (i.e. hysterectomy or bilateral oophorectomy),
 - Or
 - 3) Confirmed that all partners have had a vasectomy or tubal ligation AND have no fertile sperm based on multiple semen examinations, as shown by their medical record.

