#### 5.5.1.2. Handling of Dropouts or Missing Data

Two statistical approaches to handling missing data will be used as appropriate: repeated measures analyses and ANCOVA.

For the repeated measures analyses, the model parameters are simultaneously estimated using restricted likelihood estimation incorporating all of the observed data. Estimates have been shown to be unbiased when the missing data are MAR.

For ANCOVA model, response values at each visit will be imputed by LOCF first, then the average of 6 months (double blind period) for the response value will be derived. (Section 5.5.1.1).

Please refer to Section 5.4.1 for general approach to handling missing diary data for derivation of the number of migraine headache days and other efficacy measures (some exceptions: migraine attacks) derived from ePRO data.

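### SAP 5.4.1 ties scaling of the migraine-day count to period length and not to missed diaries, so the rule is wrong as written for a 30-day period with missed entries

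*SAP*

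**What the plan says.** The rule is in SAP 5.4.1, under the primary measure. The daily diary is added up by period and, "if the period is not equal to 30 days, the number of migraine headache days will be normalized", by multiplying it by 30/x. There x "is the total number of non-missing diary days in the period".

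Later in the same section the SAP gives the rationale: "This approach to missing ePRO diary data assumes that the rate of migraine headaches per day is the same for days with missing and non-missing" days, with the data taken to be missing at random. It extends the approach to the secondary and exploratory measures derived from the diary.

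Four other places bear on the reading:
- The opening of SAP 5.4.1: "Each month is defined as a 30-day period with migraine or headache measures normalized from the visit intervals". It makes no exception for intervals of 30 days.
- SAP 5.5.1.2: "Please refer to Section 5.4.1 for general approach to handling missing diary data for derivation of the number of migraine headache days".
- The compliance rule in SAP 5.4.1: if compliance in a month is 50% or lower, "all endpoints to be derived from the ePRO diary data for that one-month period will be considered missing". At baseline, Protocol 6.1 criterion [5] requires "completion of at least 80% of daily diary entries".
- The negative binomial sensitivity analysis in SAP 5.5.10.2, which uses the log of compliant days over 30 as an offset in every month, whatever its length.

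**The concern.** The condition and the factor measure different things. The condition looks at how long the period is; the factor corrects for how many diaries are missing. SAP 5.5.7 computes the expected diary days of a treatment month from visit dates, so the natural reading of a period is a calendar interval. A calendar interval of exactly 30 days with missed diaries then fails the condition, its raw count stands, and the missed days are in effect treated as free of migraine. That contradicts the equal-rate assumption.

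Thirty days is also the planned case. The Protocol's Schedule of Activities gives target intervals of 14+16, 30, 30, 30, 15+15 and 15+15 days for the six treatment months, and 30 days is the shortest permitted baseline. With visit tolerances of 1 to 3 days, literal coding would put scaled and unscaled months side by side in the same primary model. The primary endpoint, the response rates and most of the other diary measures are built on this count.

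**Working it through.** **Inputs.** Calendar length L: target 30 days per treatment month; 30 to 40 days at baseline (Protocol, Schedule of Activities). Smallest x in a 30-day baseline: 0.80 × 30 = 24. Smallest x in a usable 30-day treatment month: compliance must exceed 50%, and 15/30 = 50% is set to missing, so x = 16.

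**Step 1: the SAP's own example.** Visit 2 is on 1 January, the eligible day is 30 January, no diary is missing and there are 5 migraine days. L = 30, x = 30, and 5 × 30/30 = 5. Both readings give 5, so the example cannot tell them apart. The seven numbered examples concern the allocation of days to months and the compliance cut-off; none has a 30-day period with missed diaries.

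**Step 2: size in a 30-day period.** Let M be the observed count and r the true rate per 30 days.
- Literal rule: M if L = 30, otherwise M × 30/x.
- Always scaling: M × 30/x.

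Under the equal-rate assumption the expected M is r × x/30. With L = 30 the literal rule therefore understates by 1 - x/30, while always scaling returns r. With r = 8:

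| x of 30 | Literal count | Scaled count | Understatement |
|---|---|---|---|
| 27 | 7.2 | 8.0 | 10% |
| 24 (baseline floor) | 6.4 | 8.0 | 20% |
| 20 | 5.33 | 8.0 | 33% |
| 16 (treatment floor) | 4.27 | 8.0 | 47% |

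**Step 3: same missed diaries, different length.** Six missed diaries, r = 8, literal rule:
- L = 29: x = 23, expected count 6.13, times 30/23 = 8.0.
- L = 30: x = 24, expected count 6.4, left at 6.4.
- L = 31: x = 25, expected count 6.67, times 30/25 = 8.0.

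**Step 4: what can flip for one patient.**
- Response: baseline 8 (complete), then 4 days observed in 24 of 30 diaries. Literal: (8 - 4)/8 = 50%, a responder. Scaled: 4 × 30/24 = 5 and (8 - 5)/8 = 37.5%, not a responder.
- Baseline category: 7 days in 24 of 30 diaries is 7 literally (<8) and 7 × 30/24 = 8.75 scaled (≥8). SAP 5.5.1.1 and 5.5.13 use this category as a covariate, log-rank stratum and subgroup.

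**Step 5: direction.** Take true values of 8 at baseline and 5 on treatment, a reduction of 3.
- 24 of 30 diaries at baseline only: 8 × 24/30 = 6.4, and the reduction reads 6.4 - 5 = 1.4.
- 24 of 30 diaries on treatment only: 5 × 24/30 = 4, and the reduction reads 8 - 4 = 4.

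The first understates improvement and the second overstates it.

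**Step 6: between arms, by assumption only.** The documents give no observed compliance. If every month were exactly 30 days, the baseline complete and compliance c the same in all arms, the difference would be multiplied by c. The SAP's hypothetical difference of -1.5 (SAP 5.5.10.2) would become -1.425 at 95%, -1.35 at 90% and -1.20 at 80%. If compliance differed between arms, the arm that missed more treatment diaries would look better. The stated 88% power does not use this rule and is not affected.

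**The case against.** The strongest reply is that the SAP, read as a whole, already scales whenever diaries are missed. It calls the rule its approach to missing diary data, SAP 5.5.1.2 points back to it for that purpose, and the definition of a month allows no exception. Defining x by completed diaries would be odd if only calendar length mattered. For a complete 30-day month the factor is 1, so the condition may only be meant to skip a multiplication that changes nothing. And where the SAP wants missed days counted as migraine-free it says so, as it does for weekly counts in Month 1.

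Most of this stands. It makes always scaling the likelier intention, and it rules out the stronger inference a reader might draw: that the primary analysis does undercount migraine days or manufacture 50% responders. No document says that 30-day periods stay unscaled, and the 47% figure describes a single patient-month at the edge of the compliance rule, within an endpoint that averages six months. The negative binomial sensitivity analysis, with its offset in every month, would not share the fault.

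What the reply does not do is make the sentence correct. The SAP uses three conventions for missed diaries: scaling, carrying forward for migraine attacks, and counting as migraine-free for weekly counts. A programmer who codes the sentence as it stands has no worked example to show the mistake.

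**Conclusion.** The rule is wrong as written: it is a stated derivation for the primary count that gives the wrong value, on the SAP's own assumption, for a 30-day period with missed diaries. It is not established that the analysis contains this error.

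If it were coded literally, the understatement in an affected period would be 1 - x/30: 10% at 27 diaries, 20% at 24, and at most 47% in a usable 30-day treatment month. This rests on reading the period as a calendar interval and on equal migraine rates on missed and completed days. Only periods of exactly 30 days with missed diaries are touched. The bias in change from baseline has no fixed sign, and without compliance data the effect on the treatment difference cannot be computed.

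**What to change.** Replace the conditional sentence in SAP 5.4.1 with: for every period, whatever its length, the count is multiplied by 30/x, where x is the number of days in the period with a completed diary.

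Add one worked example, such as 4 migraine days in 24 completed diaries of a 30-day month, giving 4 × 30/24 = 5. Confirm that the derivation code does this for the primary count and for the other diary measures that share the rule. Leave migraine attacks (SAP 5.5.1.2) and weekly counts in Month 1 (SAP 5.4.1) to their own missing-diary rules.

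The cost is a sentence, an example and a code check. Complete 30-day periods are unchanged because the factor is 1, and periods of any other length are already scaled this way.
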